3.3.3 Limitations

The accuracy of most of these devices is limited to the degree that the secondary biometric parameters they measure are affected by factors other than IOP, such as corneal thickness (Krug, Kompa, & Schrage, 2002). The majority of the direct tonometers require use of corneal anesthetics. The greatest limitation however is that almost all of the devices are cumbersome and require skill and training to use, which in effect limits their use to the clinic /office setting.

The cost and inconvenience of the required office visits result in treatment decisions that are made based on only a few IOP measurements taken months apart. However fluctuations in IOP due to patient activity and circadian rhythm are normal. The level of imprecision in repeated IOP measurements has been estimated at +/- 5 mmHg, meaning that to be 95% certain there is any treatment effect, a difference greater than 7 mmHg must be seen between single pre- and post-treatment IOP levels (Rotchford & King, 2012). When 24 hour IOP profiles are taken, which require patients be admitted to the clinic, peak values – thought to be the most relevant for patient outcome in the long term – are seen outside of normal office hours in 80% of the cases, resulting in changes to treatment (Liang, Lee, & Shields, 2009) (Mansouri & Shaarawy, 2011).

For these reasons, alternative methods are being sought that would allow more frequent IOP assessments in the home setting.

According to company information, Sensimed Triggerfish measures a “profile of 24h ocular dimensional changes”, displayed in [arbitrary units], rather than changes in IOP in [mmHg]. To date, it is unknown how the measured changes in corneal curvature relate to IOP, especially in magnitude.

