5. JUSTIFICATION FOR THE DESIGN OF THE CLINICAL INVESTIGATION

5.1 Evaluation of pre-clinical testing/assessment

5.1.1 In-vitro Testing

5.1.1.1 *Functional Testing*

The ARGOS-IO pressure sensor is intended to remain permanently implanted and as such must retain accuracy and precision indefinitely. Six devices were subjected to simulated physiological conditions and assessed using calibrated lab reference sensors over the entire absolute pressure and temperature range. The sensor was found to have an initial drift of less than 3 mmHg per year that stabilized over time, a pressure accuracy of +/- 1.32 mmHg, and a temperature accuracy of +/- 0.14°C. Aging had no significant impact on the device (Görtz, M, 2010).

The system has been tested (01-RE-18-A) for safety in accordance with the relevant standards (ASTM F 2052 (Displacement), F 2182 (Heating), F2119-07 (Artifacts)) by means of magnetic resonance tomography (MRT) devices and found to be safe in MRT with a magnetic field strength up to 3 T. It is unlikely that there is a danger in MRT devices with higher field strengths; the manufacturer is to be contacted if an examination in such a device should be necessary.

For similar applications it was shown that an embedding of electronic components for implantation in the human body in the manner of the ARGOS-IO implant allows a stability of > 20 years (Donaldson, 1991).

Since the implant's mechanical and thermal stress after the implantation is regarded as minimal, it is assumed that a lifespan of > 10 years is achievable.

5.1.1.2 *Biocompatibility and Cytotoxicity*

The ARGOS-IO implant is intended to be permanently implanted and as such will have constant contact with tissue and tissue fluid. The three individual components of the implant (encapsulation, ASIC and micro-coil) as well as the complete implant were tested for biocompatibility and cytotoxicity.

The encapsulation material, MED-6820 silicone, which forms a hermetic seal around the ASIC and micro-coil, is the only component with which tissues are intended to have contact. This material has

	Clinical Investigation Plan ARGOS-02	Revision C <hr/> Page 38 of 106
---	---	------------------------------------

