8.4.3.2 Performance

Starting at V05, IOP level will be assessed at every follow-up visit with both GAT and the ARGOS-IO system. Measurements will be performed in series of 1 GAT measurement followed by 3 consecutive measurements with the ARGOS-IO system, with no more than 10 minutes between the GAT and the first of the ARGOS-IO system measurements in the series. Two series of measurements, one each at the beginning and end of the visit, will be made at visits 06, 08 and 10. Four series of measurements, at the beginning (1), in the middle (2) and at the end (1) will be made at each of visits 05, 07, 09 and 11. There will be a minimum of 60 minutes between the last ARGOS-IO system measurement of one series and the GAT measurement of the next.

To assess device deficiencies, at each follow-up visit site staff will record any deficiencies observed during the visit and will examine the patient's hand-held reader device and ask patients non-leading questions starting at V06 (D60) to determine if any device deficiencies occurred during the home use. To ensure accuracy and comparability of the recorded parameters, all responsible site personnel will be thoroughly instructed on the agreed measurement methods. In particular, to ensure that IOP measurements will be comparable between each patient's individual assessments as well as between the different subjects and sites.

 Implandata Ophthalmic Products GmbH	Clinical Investigation Plan ARGOS-02	Revision C
		Page 70 of 106

To assess the user acceptance of the implantation procedure and the general usability of the ARGOS-IO system, surgeons, personnel performing the ARGOS-IO system measurements and patients (self-measurement) will be asked to complete user acceptance questionnaires.

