7.3 Evaluation of Primary Performance Variables

The primary performance objective is the assessment of the agreement between measurements made using GAT and the ARGOS-IO system from V05 (day 30) through V09 (day 180). If multiple ARGOS-IO system measurements have been made at time points for which paired GAT/ARGOS-IO system measurements are to be compared, the mean of the replicate ARGOS-IO system measurements will be used for agreement evaluation. The agreement evaluation is based on the assumption, that the measurements are constant over the measurement period.

The Bland-Altman method, which compares the mean of paired measurements to their difference will be used to determine the upper and lower limits of agreement expected to contain 95% of the IOP value pairs obtained with the ARGOS-IO system and GAT. The two-sided 95% confidence intervals for each of these limits will be calculated using the Mover method (Zou, 2011) to account for repeated measurements. IOP values will be displayed as Bland-Altman plots of individual measurement pairs by measurement technique for each individual participant as well as mean plots over time (per visit and overall). This analysis is based on the FAS and is repeated for each subgroup as described in section 4.2.

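### The agreement analysis rests on pressure being constant over an undefined measurement period; if that assumption sets the variance for day 30 to 180, the limits of agreement come out too wide

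*SAP*

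**What the plan says.** SAP 7.3 covers agreement between Goldmann tonometry (GAT) and ARGOS-IO from V05 (day 30) through V09 (day 180). Where a time point has several ARGOS-IO readings, "the mean of the replicate ARGOS-IO system measurements will be used for agreement evaluation". The next sentence is: "The agreement evaluation is based on the assumption, that the measurements are constant over the measurement period". The following paragraph sets the method: "The Bland-Altman method, which compares the mean of paired measurements to their difference", used to find limits expected to hold 95% of the value pairs, with MOVER confidence intervals to allow for repeated measurements. SAP 7.5.1 repeats the averaging and constancy sentences for V10 to V11, and the protocol synopsis has them under the primary performance endpoint.

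Protocol 8.4.3.2 defines a series as one GAT reading followed by three ARGOS-IO readings, "with no more than 10 minutes between the GAT and the first of the ARGOS-IO system measurements in the series". Series are at least 60 minutes apart. There are four at V05, V07 and V09, and two at V06 and V08.

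Protocol 3.3.3 says of intraocular pressure: "However fluctuations in IOP due to patient activity and circadian rhythm are normal". Protocol 4.1 presents detection of peaks and circadian change as a purpose of the device, and 8.4.4.4 places no restriction on concomitant treatment.

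**The concern.** The subject of the constancy sentence is the whole agreement evaluation, not the averaging step. The paragraph calls a single series a time point and names only one period, day 30 to day 180. Read that way, the plan assumes that a patient's true pressure does not change for about five months, which its own protocol contradicts.

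This matters because limits of agreement with repeated measurements can be built in two ways. If the true value may vary, the variance comes from differences taken within each pair, and true change between series cancels. If the true value is taken as constant, all of a patient's readings by one method count as replicates of one quantity, and the whole within-patient spread of each method counts as that method's error. True fluctuation, which both methods see together, is then added twice instead of cancelling. MOVER supplies confidence intervals; naming it does not say which variance is meant. Two analysts following SAP 7.3 could report materially different limits.

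**Working it through.** The documents give no expected limits, SD or margin for this endpoint, so there is no planned figure to reproduce. One protocol figure can be checked: 3.3.3 puts imprecision at ±5 mmHg for repeated readings and requires a 7 mmHg change between two single readings. 5 × √2 = 7.07, which agrees.

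**Inputs**
- Series per patient, V05 to V09 (Protocol 8.4.3.2): m = 4 + 2 + 4 + 2 + 4 = 16.
- Total within-patient SD of a GAT reading: 5/1.96 = 2.55 mmHg, variance 6.51, if ±5 is a 95% range (assumption).
- ARGOS-IO error SD (Protocol 5.1.1.1, ±1.32 mmHg): 1.32/1.96 = 0.67, variance 0.454, if that is a 95% range (assumption).
- Between-patient SD of the bias, s_b: not in the documents; 2 mmHg assumed, then 1 to 2.
- SD of true within-patient pressure, s_T: not given separately; varied below. GAT error variance is then s_G² = 6.51 − s_T².

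**Model.** GAT = T + e_G; ARGOS-IO = T + patient bias + e_A.
- Paired form: V_pair = s_b² + s_G² + s_A². T cancels.
- Constant-value form: the variance of patient mean differences plus (1 − 1/m) times each method's own within-patient variance. This gives V_const = V_pair + 2 × (15/16) × s_T² = V_pair + 1.875 s_T².

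Half-width of the limits = 1.96 × √V.

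**s_T = 1, s_b = 2**
- V_pair = 4 + 5.51 + 0.45 = 9.96, half-width 6.19.
- V_const = 9.96 + 1.875 = 11.84, half-width 6.74.
- Ratio 1.09.

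**s_T = 2, s_b = 2**
- V_pair = 4 + 2.51 + 0.45 = 6.96, half-width 5.17.
- V_const = 6.96 + 7.5 = 14.46, half-width 7.45.
- Ratio 1.44. Limits meant to hold 95% of differences would hold about 99.5%.

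These lines use the error of a single ARGOS-IO reading. The SAP averages three, so s_A² becomes 0.454/3 = 0.151. The ratios are then 1.09 and 1.46.

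**Range.** With three readings averaged and s_b from 1 to 2, splitting the 6.51 between true variation and GAT error gives:

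| True share of within-patient variance | Paired half-width (mmHg) | Constant-value half-width (mmHg) | Excess |
|---|---|---|---|
| 0% | 5.4 to 6.4 | 5.4 to 6.4 | 0 |
| 25% | 4.8 to 5.9 | 5.9 to 6.8 | 16 to 23% |
| 50% | 4.1 to 5.3 | 6.4 to 7.2 | 35 to 54% |
| 75% | 3.3 to 4.7 | 6.8 to 7.6 | 61 to 107% |

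Fixing GAT error instead (s_G = s_b = 1.5), the paired half-width stays at 4.23 for every s_T, while the constant-value one is 5.01 at s_T = 1 and 6.83 at s_T = 2. A simulation of 22 patients with 16 pairs each agreed with the algebra to within 0.05 mmHg.

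**The case against.** The best defence is that the constancy sentence belongs to the averaging instruction before it. Averaging three readings at a time point needs the pressure to hold still for those few minutes. The sentence travels with that instruction into SAP 7.5.1 and the synopsis, and SAP 8.2 reports an interim rerun using the first ARGOS-IO reading in place of the mean, which probes exactly this averaging. The method paragraph then describes paired differences, and neither document contains a constant-value formula. All of this stands as a plausible account of intent, and it is why the inflation is conditional. It does not make the wording safe, because the sentence as written governs the whole evaluation and leaves its period undefined.

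Four stronger readings are tempting, and the documents do not support them:
- **Pooling day 30 to 180 by itself widens the limits.** It does not. Each difference is taken within a series, so true change between series and visits cancels.
- **An analyst would necessarily choose the constant-value form.** That depends on how the sentence is applied and on a cited methods paper that is not part of the documents.
- **Sensor drift makes the limits too wide.** Protocol 5.1.1.1 reports a bench result: "The sensor was found to have an initial drift of less than 3 mmHg per year that stabilized over time". Over 150 days that is at most 3 × 150/365 = 1.2 mmHg. Drift is real device disagreement and belongs in the limits.
- **A pass/fail decision is at risk.** SAP 5.3 says the performance variable is not tested, and no margin is set.

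A change in bias over time would also not go unseen: SAP 7.3 plans plots per visit and overall, and the SAP table list includes limits over time.

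**Conclusion.** The concern holds in conditional form. The plan states a constancy assumption that is untenable over the only period named with it, and it does not say which variance form underlies the limits. If the constant-value form is applied over V05 to V09, the limits are too wide: about 9% at a true-pressure SD of 1 mmHg and 44% at 2 mmHg, with a between-patient bias SD of 2 mmHg. If within-series paired differences are used, the excess is zero apart from any change inside a series.

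The added term, 1.875 s_T², follows from the design. The percentages do not: the split of the ±5 mmHg, the bias SD and the reading of both ± figures as 95% ranges are assumptions. The consequence is misreported precision. That still deserves correction, because without a margin the limits and their intervals are the main co-primary performance result.

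**What to change.** In SAP 7.3 and 7.5.1, and in the protocol synopsis if it is amended again, replace the constancy sentence with:

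> True IOP is assumed constant only within a series and may vary between series and visits. Limits are computed from the within-series paired difference (mean ARGOS-IO minus GAT) with between-patient and within-patient variance components of the difference, and MOVER confidence intervals for that varying-true-value form.

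The by-visit limits and plots already planned should stay. SAP 8.2 records limits per visit and overall at the first sponsor interim analysis, and the same set of reports after Visit 9. The SAP should therefore also state which form those used, so that the final choice is not seen as made after the results were known.

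The cost is a wording change and, if the constant-value form was programmed, a different variance formula on the same data. The SAP is to be signed before hard lock, so this can be settled there. If paired differences were always intended, the change only records that.

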7.4 Evaluation of Secondary Safety Variables

Safety will be described in detail by frequency, seriousness, severity, nature and duration of adverse events based on the safety evaluation set. Number of adverse events as well as the number and relative frequency of patients reporting adverse events will be tabulated by system organ class and preferred terms. The same table will be prepared for serious adverse events. In addition, the number and relative frequency of patients reporting adverse events will be tabulated by system organ class and preferred terms in dependence on the worst severity and worst causal relationship. Furthermore, number of adverse device effects as well as the number and frequency of patients reporting adverse device effects will be tabulated by system organ class and preferred

terms and not by event description as stated in the protocol. Separate tables will be provided for events occurring 3, 6 and 12 month following implantation.

SADEs. SAEs leading to discontinuation as well as the nature and duration of AEs will be provided in listings only. The duration of adverse events will be calculated as follows:

$$\text{Duration of AE} = \text{Stop date of AE} - \text{Start of AE} + 1.$$

7.5 Evaluation of Secondary Performance Variables

All secondary performance variables will be analysed on the basis of the FAS population.

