8.1.5 Any procedures for the replacement of subjects

Screen failures (withdrawn for any reason up to implant) will be replaced. Subjects who withdraw their consent after implantation will not be replaced.

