8.4.4.6 Device Malfunctions

Starting with the implantation of the ARGOS-IO system IOP measurements at V05 (D30), all observed device malfunctions will be recorded.

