8.7.2 Surgery, Visit 1 (Day 0)

The following procedures may be carried out one day before surgery (in subjects already hospitalized for the surgery) or on the day of surgery:

- Verify that the subject continues to meet eligibility criteria
- For female subjects of childbearing potential: collect urine for pregnancy test. A test done within 24 hours prior to surgery must be negative
- Perform external eye photography prior to surgery.

The following procedures are to be performed on the day of the surgery:

- Cataract surgery and ARGOS-IO pressure sensor implantation as described in section 8.5, including the recording of any AEs, SAEs starting from implantation of the ARGOS-IO pressure sensor; any concomitant medication related to SAE/SADEs during surgery; and any device malfunctions.
- Completion of the implantation procedure questionnaire (surgeon) and the CRF
- Complete the patient inclusion form and fax it to the sponsor
- Instruct subjects on the need to report promptly any SAE that may occur at any time during the study.
- Arrange a date for Visit 2 (V02).
- The duration of the patient's hospitalization is at the discretion of the Investigator. Recommended duration is 1 to 3 days, but durations of up to 7 days will not be considered in themselves to be SAEs.

 Implandata Ophthalmic Products GmbH	Clinical Investigation Plan ARGOS-02	Revision C
		Page 78 of 106

8.7.3 Follow-up visits 02 to 04 (early post-surgical): days 1, 3 and 10

Procedures to be conducted at the early post-surgical visits include:

- Visual acuity
- External eye photography
- Recording of AEs/SAEs/ADEs/SADEs, concomitant medications (all)
- Anterior Segment Measurements: Slit-lamp microscopy only
- Posterior Segment Measurements: Biomicroscopy only
- IOP Measurement (GAT only)
- Complete the CRF and arrange the next visit.

8.7.4 Follow-up visits 05 to 11: days 30, 60, 90, 120, 180, 240 and 360

Procedures to be conducted at the early post-surgical visits include:

- Visual acuity
- Perimetry (Visits 07, 09 and 11 only)
- External eye photography
- Recording of AEs/SAEs/ADEs/SADEs, concomitant medications (all)
- Anterior Segment Measurements:
 - Slit-lamp microscopy at all visits
 - AS-OCT, gonioscopy and confocal microscopy at V07, V09 and V11
- Posterior Segment Measurements:
 - Biomicroscopy at all visits
 - PS-OCT, gonioscopy and fundus photography at V07, V09 and V11
- IOP Measurement: GAT and ARGOS-IO system
 - 4 series at visits 05, 07, 09 and 11

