4.1 Analysis Populations

Within the framework of this study, the following two main populations are analysed:

- **Safety Population:** consists of all patients with attempted implantation of the ARGOS-IO implant, whether or not successful.
- **Full Analysis Set (FAS):** The FAS population comprises all subjects in whom an ARGOS-IO pressure sensor was successfully implanted. Measurements recorded by the patient will not

be included into the evaluation of the FAS population. Additional information about the drop-outs: all patients who revoke their consent and agreement preoperatively will be regarded as screen failures and will not be included in the statistical evaluation. All patients who revoke their consent and agreement postoperatively will be considered withdrawals and their data will be evaluated in the safety analysis.

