6.5 Secondary Performance Variables

Assessment of the secondary performance variables include

- Limits of agreement between IOP measurements made using GAT and the ARGOS-IO system from Visit 10 through Visit 11
- Incidence of observed of device malfunctions in the 3, 6 and 12 months following implantation
- User acceptance of the implantation procedure by means of evaluation of the implantation procedure questionnaires (investigators)
- User acceptance of the ARGOS-IO system at the investigational site by means of evaluation of the investigator acceptance questionnaires (investigators)
- User acceptance of the ARGOS-IO system at home by means of evaluation of patient acceptance questionnaires (patients) at Visit 11
- Daily IOP self-measurement profiles (patients).

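### Device malfunction incidence and acceptance of the implantation procedure are analysed only in successfully implanted patients, so a malfunction that ends an implantation attempt is left out of both

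*SAP*

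**What the plan says.** **Variables and analysis set**

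- SAP 6.5 lists among the secondary performance variables "Incidence of observed of device malfunctions in the 3, 6 and 12 months following implantation", and the investigators' acceptance of the implantation procedure as measured by questionnaire.
- SAP 7.5 sets the population for the whole group: "All secondary performance variables will be analysed on the basis of the FAS population". The subsections on malfunctions (7.5.2) and on the procedure questionnaire (7.5.3) name no other set.
- SAP 4.1 defines that set: "The FAS population comprises all subjects in whom an ARGOS-IO pressure sensor was successfully implanted". The safety population in the same section is wider; it "consists of all patients with attempted implantation of the ARGOS-IO implant, whether or not successful". The CIP synopsis also counts attempts, but CIP 9.11.1 limits the safety evaluation to successful implantations.

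**Patients who are not implanted**

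- CIP 8.5.2 lets the surgeon stop the sensor implantation whatever the reason. CIP 8.3.3.3 and SAP 2.6 list non-feasibility found at surgery as a reason for withdrawal.
- CIP 8.1.5: "Screen failures (withdrawn for any reason up to implant) will be replaced". The synopsis counts the recruitment target of 22 in implanted patients.

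**Start of malfunction recording**

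- CIP 8.4.4.6: "Starting with the implantation of the ARGOS-IO system IOP measurements at V05 (D30), all observed device malfunctions will be recorded".
- CIP 8.7.2, for the day of surgery, includes "any concomitant medication related to SAE/SADEs during surgery; and any device malfunctions". The CIP synopsis, CIP Table 6 and SAP Table 1 also start at V01. CIP 11.1.5 asks for all observed deficiencies and gives no start day.

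**The concern.** The investigational system includes the injector as well as the implant (CIP synopsis and 4.1). If either fails so that the attempt has to be given up, that is a failure of device performance. It is also the kind of event that the malfunction endpoint and the procedure questionnaire are there to register. Restricting both to patients in whom insertion succeeded removes such an event from the numerator and the patient from the denominator. A replacement patient can then fill the place.

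The plan itself foresees failed attempts. SAP 4.2 names successful implantation (yes or no) as a subgroup. Yet SAP 7.3 runs the performance subgroups on the FAS, where the "no" group is empty by definition.

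At stake is the credibility of two descriptive secondary measures, not the primary safety decision. With only 22 patients, a single omitted event moves the reported rate visibly.

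**Working it through.** **Plan's own figure.** The documents state no malfunction rate, expected or observed, and no number of failed attempts. There is nothing to reproduce; the only input taken from the plan is the target of 22 implanted patients.

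**What is counted where**

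| Event | In FAS analysis? | In safety population (SAP 4.1)? |
|---|---|---|
| Malfunction ends the attempt, no sensor implanted | No | Yes |
| Malfunction at surgery, sensor still implanted | Yes | Yes |
| Malfunction during follow-up of an implanted patient | Yes | Yes |
| Surgeon's questionnaire for an abandoned attempt | No | Yes, if completed |

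On the last row, CIP 8.4.4.7 asks for the form after each implantation, so it may not be completed for an abandoned attempt.

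**Formula.** Let m be the number of patients with a malfunction among the 22 implanted. Let k be the number of attempts ended by a malfunction and replaced. Assume no attempt is abandoned for any other reason.

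- FAS rate = m/22
- Rate on all attempts = (m + k)/(22 + k)
- Difference = [22(m + k) − m(22 + k)] / [22(22 + k)] = k(22 − m) / [22(22 + k)]

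The difference is zero when k = 0. It is positive whenever k ≥ 1 and m < 22, so under this assumption the FAS rate can only be too low.

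**Numbers** (k is assumed; exact Clopper-Pearson 95% intervals are given for m = 0)

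| k | FAS, m = 0 | All attempts, m = 0 | FAS, m = 1 | All attempts, m = 1 |
|---|---|---|---|---|
| 0 | 0/22 = 0% (0 to 15.4%) | 0/22 = 0% (0 to 15.4%) | 1/22 = 4.5% | 1/22 = 4.5% |
| 1 | 0/22 = 0% | 1/23 = 4.3% (0.1 to 21.9%) | 1/22 = 4.5% | 2/23 = 8.7% |
| 2 | 0/22 = 0% | 2/24 = 8.3% (1.0 to 27.0%) | 1/22 = 4.5% | 3/24 = 12.5% |
| 3 | 0/22 = 0% | 3/25 = 12.0% (2.5 to 31.2%) | 1/22 = 4.5% | 4/25 = 16.0% |
| 4 | 0/22 = 0% | 4/26 = 15.4% (4.4 to 34.9%) | 1/22 = 4.5% | 5/26 = 19.2% |

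Each such attempt adds about four percentage points on the wider set and nothing on the FAS. An attempt abandoned for a reason in the patient, not the device, would add only to the wider denominator.

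**The case against.** **Case for leaving the plan as it is**

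- *The endpoint is timed from implantation, so a patient without an implant has no 3-, 6- or 12-month window.* That is a fair reading for follow-up malfunctions. It does not justify omitting a failure of the injector or implant at the operation itself.
- *Spare devices are supplied (CIP 4.5; about 90 devices in CIP 8.2.4).* This stands in part. If a defective unit is exchanged and implantation succeeds, the patient is in the FAS and the event counts. Only malfunctions that end the attempt are lost.
- *Failed attempts show up elsewhere.* True: SAP Tables 31 and 35 and Listings 20, 24, 31 and 34 cover surgical complications, implantation, questionnaires and deficiencies. A malfunction that causes harm is also an adverse device effect (CIP 11.1.2.1). None of these corrects the reported incidence, and a harmless failure to implant is not an adverse device effect.
- *The measures are descriptive, and CIP 8.4.4.7 says questionnaire data stay out of the analysis.* The first part limits the weight of the point. The second conflicts with CIP 8.1.3.2 and SAP 7.5.3, which make the questionnaire an endpoint and tabulate it.

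**Stronger readings that the documents do not support**

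- A reader might infer that malfunctions which merely complicate a successful implantation are also lost. They are not: the patient is in the FAS and the event is collected at V01 under CIP 8.7.2 and both schedule tables.
- A reader of CIP 8.4.4.6 might infer that the first 30 days go unrecorded. That rests on one garbled sentence, contradicted by the synopsis, 8.7.2, Table 6, 11.1.5 and SAP Table 1. The SAP also cites CIP Rev. G, while the text available is Rev. C with an addendum, so the sentence may since have changed. It is a contradiction to resolve, not an established gap.
- A reader might infer that insertion is what was mainly redesigned after ARGOS-01, notably that folding is new. CIP 5.3 does mention a cartridge injector and protrusions to ease unfolding, but it presents the injector as a related procedural change and gives less irritation and pressure drift as the expected gains. Folding already featured in the porcine-eye tests (CIP 5.1.1.5).

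**Conclusion.** The point holds for malfunctions that end an implantation attempt. They, and the surgeon's questionnaire for that attempt, fall outside the two measures by the plain combination of SAP 7.5, 6.5 and 4.1.

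If any such attempt occurs, the reported incidence is too low: 0% instead of 4.3% for one event or 8.3% for two. This assumes 22 implanted patients, no other malfunction and no attempt abandoned for other reasons. If no attempt is abandoned, the sets coincide and nothing changes. Bias is therefore a possibility built into the definition, not an established fact, and its size is unknown because the documents give no counts. At this sample size the exact intervals overlap heavily (0 to 15.4% against 0.1 to 21.9% for one event).

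The change should be made, but it touches secondary descriptive results only. The analysis-set problem lies in the SAP itself and does not depend on which CIP revision applies.

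**What to change.** 1. In SAP 7.5, 7.5.2 and 7.5.3, analyse device malfunctions and deficiencies, and the implantation procedure questionnaire, on the SAP safety population. Show malfunctions at surgery as a separate row. Keep the FAS for limits of agreement.
2. Have the surgeon complete the questionnaire after each attempt, whether or not the sensor stays in, and reconcile the CIP 8.4.4.7 statement on its use with CIP 8.1.3.2 and SAP 7.5.3.
3. Reconcile CIP 9.11.1 with SAP 4.1 and the CIP synopsis, so that the safety set has one definition before the two variables are moved to it.
4. Reconcile the recording start in CIP 8.4.4.6 with the synopsis, 8.7.2, Table 6, 11.1.5 and SAP Table 1. A row for malfunctions at surgery requires recording from V01.

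The cost is wording in the SAP and CIP; the forms exist, and the SAP is to be signed before hard lock of the database. A questionnaire not collected for an abandoned attempt would have to be obtained or shown as missing. The malfunction rate may become slightly less favourable.
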